## 1. SYNOPSIS

Study Title	Optimizing outpatient anesthesia
Objective	
In separate cohorts of patients undergoing moderately painful outpatient surgery (“short-stay” requiring overnight hospitalization with intended next day discharge and “same-day” surgery), compare the influence of general anesthesia with long-duration vs short-duration opioids on
 
 
1. short-term (before discharge) and intermediate term (1-30d post-discharge) opioid consumption.
 
2. short-term (immediate postoperative), intermediate term (1-30d post-discharge), and chronic (6 and 12 mo) postoperative pain.
 
3. short-term (immediate postoperative), intermediate term (1-30d post-discharge) opioid-related side effects
 
4. intermediate (30d post-discharge), and long-term (6 and 12 mo) quality of recovery.
 

Study Period	
Approximately 30 days per subject, plus 6 and 12 month follow-up  Total enrollment duration: Approximately 4 years

Number of Patients	
600 evaluable subjects. Estimated number to be studied is 750 with 25% loss to follow-up.  Estimated enrollment is 1000 to account for schedule changes, withdrawals, etc.

Inclusion and Exclusion Criteria	
Inclusion Criteria
 
 
1. Age 18-65 years
 
2. Undergoing general anesthesia and moderately painful ambulatory surgery with anticipated postop stay of < 24 hours
 
3. Signed, written, informed consent
 
 
Exclusion Criteria
 
 
1. History of liver or kidney disease.
 
2. Females who are pregnant or nursing.
 
3. Chronic opioid use (e.g. preoperative daily use of methadone, buprenorphine, fentanyl transdermal patches, or <math>\geq 3</math> oxycodone pills)
 

Study Design	
Single-center, randomized, double blinded, parallel-group, 2-cohort investigation. Patients receive standard monitoring for anesthesia and postoperative care. Surgical and anesthesia care (except for intraoperative opioid use) are not altered for study purposes. In each cohort, subjects are randomized 1:1 to either long-duration opioid (IV methadone HCl) or typical short-duration opioid (IV e.g. fentanyl, morphine or hydromorphone at anesthesia provider discretion) intraoperatively and postoperatively in the recovery room. Intraoperative methadone doses are 15 mg in “short-stay” patients (10 mg if <math>\leq 55</math>kg) and 10 mg in “same-day” surgery patients.

Study Drug Administration	
In each of two cohorts (“short-stay” and “same-day” outpatients), 375 patients are randomized 1:1 (187 each) to receive long-duration opioid (IV methadone HCl) or typical short-duration opioid (e.g. fentanyl, morphine or hydromorphone at anesthesia provider discretion) intraoperatively & postoperatively in the recovery room (PACU).

Measurements	
Patients complete a questionnaire about current pain, past 7 day average pain, pain interference with activities of daily living, and expected level of postoperative pain. Total intraoperative and postoperative opioid administration during hospitalization will be recorded from the medical record. Pain intensity will be assessed using a verbal Numeric Rating Scale (NRS). Pain relief will be assessed using five point scale (0-no relief, 4-complete pain relief). Postoperative sedation will be recorded using Modified Observer’s Assessment of Alertness/Sedation (MOAA/S). Opioid-related side effects will be assessed using the Opioid-Related Symptom Distress Scale (ORSDS). Daily opioid consumption and pain self-assessments using a NRS and ORSDS will be recorded for approximately 30

	
days after surgery using anemailed REDCap or paper survey tool. Pain (PROMIS Pain Intensity and Pain Interference) and recovery (patient-reported quality of life, functional independence, health status, ability to return to work and normal activities; PROMIS global health, PROMIS-29, Veterans RAND 12-item VR-12 survey, Barthel index of activities of daily living, Quality of Recovery QoR-15) will be assessed at 7d, 14d, 21d, 30d, 6mo and/or 1yr postoperatively. Blood will be collected for future DNA analysis (CYP2B6 or pain-related genes).

Statistical Methodology	
Both cohorts are analyzed separately. Demographic data including race, sex, and age will be analyzed using chi-square. Post-discharge opioid use (30d) is compared using Chi-square tests and multiple logistic regression, with opioid group as a predictor and adjusting for covariates. Total pill consumption is compared with a GEE model and Poisson link function. A time-to-event (survival) model will compare time to opioid discontinuation. Opioid use during intraop, in-hospital post-op, and post-discharge periods will be evaluated using appropriate model and data transformation. Pain reduction effectiveness of long- vs short-duration opioids is compared using repeated measures models to adjust for multiple measures on each subject. Side effects will be compared using Chi-squared or Fisher exact tests. Overall recovery will be assessed using chi-square tests for categorical outcomes and t-tests for continuous outcomes as well as a repeated measures model.

Outcomes	
Primary: total 30d post-discharge home opioid use (number of tablets)
 
Secondary:
 
 
1. Total 7d post-discharge home opioid use
 
2. Total intraoperative non-methadone opioid administration
 
3. Total PACU opioid administration
 
4. Total hospital non-methadone opioid administration
 
 
Exploratory:
 
 
1. Total day of surgery nonmethadone IV opioid administration
 
2. Total day of surgery nonmethadone IV and oral opioid administration
 
3. Total day of surgery opioid administration
 
4. Postoperative day 1 total IV oral and opioid administration (short-stay cohort only)
 
5. Total hospital opioid administration
 
6. PACU pain scores (NRS) and pain relief score; at time-specific intervals
 
7. Duration of intraoperative analgesia (median time to request for re-medication with opioid)
 
8. PACU side effects and adverse events: respiratory depression (4 events occurrence per above), sedation (MOAA/S score), nausea/vomiting (number of events); at time-specific intervals and total
 
9. PACU duration of stay
 
10. 7d and 30d total post-discharge home opioid use (in morphine equivalents)
 
11. 7d and 30d post-discharge pain scores (NRS) and pain relief score; daily
 
12. Total pain relief, calculated as the area under the curve of pain relief score vs time
 
13. 7d and 30d post-discharge opioid side effects (ORSDS); daily, weekly and total (summed and average)
 
14. Time to cessation of post-discharge opioid use
 
15. 7d and 30d post-discharge unused opioid tablet count
 
16. Quality of recovery at 7d, 14d, 21d, 30d, 6 mo, and/or 12 mo (PROMIS global health, PROMIS-29, VR-12, Barthel index, QoR-15, functional independence, return to work)
 
17. Surgeons' opioid prescribing patterns
 

## 2. STUDY PROTOCOL

### 2.1 Background and Significance

Anesthesiologists and surgeons face two challenges: (1) More than 80% of surgical patients report inadequately treated pain. Chronic postsurgical pain develops in 10-50%, and acute postoperative pain is the single greatest risk factor. Treating pain in outpatient surgery is particularly challenging. Unfortunately, no meaningful progress has been made in postsurgical pain treatment in the last 20 yr. (2) The USA is awash in opioids, with skyrocketing prescribing, diversion, abuse, addiction, and fatal overdose. There is a growing reservoir of unused opioids (some originally prescribed for postoperative pain) being diverted and misused. Shrinking the opioid pool is a public health imperative,

Opioids remain the primary therapy for intraoperative and postoperative analgesia. Over the past decades progressively shorter-duration opioids have been used intraoperatively. In contrast, accumulated evidence strongly establishes that a single intraoperative dose of a long-duration opioid (i.e. methadone), which sustains therapeutic drug concentrations, produces better analgesia than repeated doses of short-duration opioids, and reduces further opioid requirements. Nevertheless, this has only been evaluated for inpatients.

Intraoperative anesthesia and postoperative analgesia are most commonly achieved with the opioids morphine, hydromorphone, fentanyl, and methadone. Methadone has several therapeutic advantages compared with these other opioids, including more rapid onset, absence of active metabolites, lack of P450 (CYP2B6) genetic influence on the disposition of intravenous methadone, and longer elimination half-life and duration of effect. For example, the elimination half-life of methadone is 1-2 days, compared with remifentanil (0.5 hr), morphine and hydromorphone (2-3 hr), and fentanyl (8-10 hr), although the actual duration of effect of these latter opioids is much shorter due to rapid redistribution. Methadone is both a  $\mu$ -opioid receptor agonist and an N-methyl-D-aspartate (NMDA)-receptor antagonist, which may confer additional therapeutic benefit. In addition, even when given intraoperatively, even in a single dose, methadone, compared with shorter-duration opioids, results in lower pain intensity, better postoperative pain relief, longer duration of analgesia, and, *of particular importance and relevance to the opioid epidemic*, need for fewer postoperative opioid doses, and lower cumulative postoperative opioid use. Moreover, these clinical advantages do not come at a cost of greater opioid side effects (respiratory depression, nausea, vomiting).

### 2.2. Preliminary Data

We conducted two WUSTL IRB-approved (201408002), prospective, randomized, double-blind clinical pilot studies, with separate outpatient cohorts (both termed outpatients per CMS definitions; Medicare Benefit Policy Manual, Chapter 6, Rule 20.2).

[figure not shown]
- Patients undergoing short-stay (overnight stay, <24 hr) outpatient surgery
- Patients undergoing true same-day discharge outpatient surgery

Two cohorts were studied because their operations may have different pain intensities and opioid requirements. Inclusion and Exclusion Criteria were identical to those for the present investigation. Subjects were randomized to receive short-duration (IV fentanyl, morphine or hydromorphone at anesthesia provider discretion) or a single dose of a long-duration (IV methadone HCl) opioid intraoperatively. Because methadone anesthesia for outpatient surgery had not previously been studied, these pilot studies used escalating dose groups (typically ~20 per group) to determine the optimal methadone dose for each cohort (short-stay, same-day). The methadone bolus at anesthetic induction was 0.1, 0.2, 0.25, or 0.3 mg/kg ideal body weight for short-stay cases and 0.1 or 0.15 mg/kg ideal body weight for same-day cases. The specific objective was to evaluate intraoperative, immediate postoperative (Post-Anesthesia Care Unit, PACU), and 30d postoperative opioid consumption; immediate and 30d postoperative pain intensity and pain relief; and postoperative opioid-related side effects. And to determine the optimal dose for subsequent large-scale studies.

Results for the short-stay surgery (<24hr) cohort show that a single intraoperative methadone dose ( $17 \pm 2$  mg) reduced intraoperative and post-operative in-hospital opioid requirement. Average PACU opioid use was  $4 \pm 5$  mg morphine equivalents after  $17 \pm 2$  mg/kg methadone (not different vs other groups). Methadone did not cause any greater postop sedation or other adverse effects (nausea, emesis). Based on these preliminary intraoperative + PACU opioid use data, a single 15 mg intraoperative dose of methadone will be used in this protocol for the short-stay surgery (<24hr) cohort. This is the typical dose for patients staying in the hospital.

Results for the same-day surgery cohort showed that a single intraoperative methadone dose ( $9 \pm 1$  mg) reduced intraoperative, PACU, and post-operative opioid requirement. Average PACU opioid use was  $2 \pm 3$  mg morphine equivalents after  $9 \pm 1$  mg methadone. A single intraop methadone dose also decreased 30d postop opioid use, with less opioids consumed and earlier cessation of use. Despite using less opioid, 30d pain scores were no different in the patients receiving methadone. Patients receiving intraop methadone were also more comfortable (less pain) on arrival in PACU. Methadone did not cause any greater postop sedation or other adverse effects (nausea, emesis). Based on these intraoperative + PACU opioid use preliminary data, a single 10 mg intraoperative dose of methadone will be used in this protocol for the same-day surgery cohort.

Because methadone has a longer elimination half-life, there is natural and appropriate concern about potential respiratory depression. Studies published to date show that postop respiratory effects of methadone are *no different* than other opioids. The above studies found similarly. Nevertheless, we also performed a large-scale QA analysis. We reviewed 3 yr of general anesthetics (n=154,249) with regard to the intraoperative opioid and side effects and safety (Figure). There was no difference between patients receiving methadone (and no methadone dose-effect relationship) vs other opioids (e.g. morphine, fentanyl, hydromorphone) with regard to PACU discharge (duration of stay), nausea/emesis (using antiemetic therapy as an indicator), or respiratory depression (using naloxone administration as an indicator). Thus, we are fully assured of methadone safety for outpatient anesthesia.

Retrospective QA analysis of opioid safety and side effects in general anesthesia (n=154,249 over 3 yr). There was no difference between pts receiving methadone (and no methadone dose-effect relationship) vs other, short-duration opioids (e.g. morphine, fentanyl, hydromorphone) intraoperatively with regard to (left) PACU discharge time (duration of stay), (center) nausea/emesis (using antiemetic therapy as an indicator), or (right) respiratory depression (using naloxone administration as an indicator).

### 2.3. Objective

The overall goal of this research is to improve perioperative pain treatment, decrease post-operative opioid consumption, diminish opioid related side effects, and reduce postop opioid prescribing (and hence opportunity for diversion, abuse, addiction, and fatal overdose). This protocol will test the innovative, paradigm-shifting hypothesis that anesthesia for outpatient surgery with long-duration opioids (methadone), compared with conventional short-duration opioids, achieves better analgesia, with similar or diminished side effects, may reduce development of chronic postsurgical pain, improves recovery, and importantly, decreases postoperative opioid consumption and could hence diminish take-home opioid prescribing and shrink the population reservoir of unused opioids available for diversion and misuse.

Specific Aims: In separate cohorts of patients undergoing moderately painful outpatient surgery (“short-stay”

requiring overnight hospitalization with intended next day discharge and “same-day” surgery), compare the influence of general anesthesia with long-duration vs short-duration opioids on

1. short-term (before discharge) and intermediate term (1-30d post-discharge) opioid consumption.
2. short-term (immediate postoperative), intermediate term (1-30d post-discharge), and chronic (6 and 12 mo) postoperative pain.
3. short-term (immediate postoperative), intermediate term (1-30d post-discharge) opioid-related side effects
4. intermediate (30d post-discharge), and long-term (6 and 12 mo) quality of recovery.

In ambulatory surgery patients, methadone is expected to decrease the need for additional opioids in the immediate postoperative period, decrease 30d opioid consumption, decrease opioid-related side effects, improve postoperative pain relief, decrease the occurrence of chronic postoperative pain, reduce opioid quantities routinely prescribed upon discharge, and improve overall patient recovery

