### 2.7 Sample size justification

Sample size is based on the primary outcome measure, total 30d post-discharge home opioid use (number of opioid tablets). Based on available reports (Background) and the Preliminary Results, an ideal state of post-discharge opioid use is defined as  $\leq 5$  pills in 30 days. In the Preliminary data, the rate of "high" post-discharge opioid use (defined as  $> 5$  pills in 30d) was 45% in the short-duration opioid group. With a conservative assumption of a relative risk of 65% for the long-duration group (30% rate of "high" opioid use), a total of 300 subjects (150 per group) will be needed to achieve 80% power assuming alpha = 0.05.

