**Aim 3:** Evaluate major and bothersome short-term (before discharge) and intermediate term (1-30d post-discharge) opioid-related side effects with methadone vs short-duration opioids.

Side effects (respiratory-specific events, composite ORSDS) will be compared between the groups using Chi-squared or Fisher exact test, as appropriate, and using logistic models to adjust for important clinical and demographic covariates.

**Aim 4:** Compare overall recovery after surgery/anesthesia with methadone vs short-duration opioids, as defined by changes in reported Health-related Quality of Life, functional independence, and ability to return to work and normal activity.

Overall recovery will be assessed using chi-square tests for categorical outcomes and t-tests for continuous outcomes as well as a repeated measures model to adjust for multiple time points.

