### **3.0 Recruitment strategy and feasibility**

Subjects will be 18-65 yr. Because this is the first evaluation of methadone for outpatient anesthesia, children and older patients will not be studied (because of declining methadone elimination and increased risk of respiratory depression with age). Such studies may ensue after safety is established in the present investigation. Sample size calculations show that 300 evaluable (completing 30d follow-up) patients are needed in each of the 2 study cohorts (600 total). Change in scheduled operation, prolonged ( $>1$ d) stay of scheduled short-stay (next day discharge) patients, unanticipated admission of same-day patients, or patient withdrawal has occurred in  $\sim 10\%$  of our study patients to date. This, combined with post-op loss to follow-up (see below), suggests a potential overall drop-out rate before completion of 30d follow-up of  $<15\%$ . Hence, to ensure 300 pts evaluable at 30d, a conservative 25% drop-out is estimated and 375 pts in each of the 2 study cohorts will be randomized (750 total). The Duke Department of Anesthesiology provides anesthetics for  $>66,000$  procedures per year. The main campus of Duke University Health System includes Duke University Hospital which is a 957 bed facility. In 2016 there were 41,408 patients admitted and 1,119,151 outpatient visits. Duke University Hospital includes the Duke North Hospital/Duke Medical Pavilion ( $\sim 54$  ORs), the Children’s Health Center, the Duke Eye Center (6 ORs), and Ambulatory Surgery Center (9 ORs). Between the Duke North Hospital/Duke Medical Pavilion and Ambulatory Surgery Center there were 34,492 anesthetics performed in 2017. These included, for example, 375 laparoscopic cholecystectomies and 269 laparoscopic hysterectomies  $\pm$  salpingoophorectomies, further supporting specific feasibility. If enrollment lags, or for strategic advantage, Duke Regional and/or Duke Raleigh Hospitals can be added as future sites.

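### The hypothesis includes similar side effects, but the planned side-effect analyses look only for differences and state no interval criterion, so a non-significant result could not show similarity or establish safety

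*Combined protocol and SAP*

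**What the plan says.** - **Hypothesis (section 2.3).** Methadone, compared with short-duration opioids, "achieves better analgesia, with similar or diminished side effects". The same section later expects methadone to "decrease opioid-related side effects, improve postoperative pain relief". Side effects thus carry two claims: similar or lower, and lower.
- **Safety (section 3.0).** Children and older patients are left out of this first outpatient evaluation because of declining methadone elimination and greater respiratory risk with age. The text continues: "Such studies may ensue after safety is established in the present investigation".
- **Analysis.** The Synopsis says "Side effects will be compared using Chi-squared or Fisher exact tests". Section 2.8, Aim 3, covers respiratory-specific events and the composite symptom distress score; the stated method is that they are "compared between the groups using Chi-squared or Fisher exact test, as appropriate, and using logistic models to adjust for important clinical and demographic covariates". The cohorts are analyzed separately (sections 2.4 and 2.8).
- **Status and size.** Respiratory events in the recovery room and post-discharge side effects are exploratory outcomes 8 and 13 (section 2.6.8). For the trial's size, "Sample size is based on the primary outcome measure, total 30d post-discharge home opioid use" (section 2.7). No power statement, margin or confidence-interval criterion is given for any side effect.

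**The concern.** A test for a difference can give evidence of harm or of benefit. When it is not significant, it does not separate two arms with nearly equal rates from two arms with too few events to compare. The word similar in section 2.3 needs the first of these, and nothing in the analysis section supplies it.

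Respiratory depression is where this matters most. Section 2.6.7 ranks it first among opioid-related adverse events, and section 2.2 accepts that methadone's long half-life makes the worry reasonable. Section 3.0 then links possible later studies, including in older patients whom the protocol regards as at higher respiratory risk, to safety having been shown here. If the only evidence were a non-significant p-value, that link would be unsupported.

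There is some reason to expect such a reading. Section 2.2 reports no difference in pilot groups of typically about 20 patients and in a retrospective review of 154,249 anesthetics, and concludes from this that methadone's safety in outpatients is fully assured.

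**Working it through.** **1. The plan's own figure.** Section 2.7 takes high opioid use (more than 5 pills) in 45% of controls, a relative risk of 0.65, alpha 0.05 (two-sided assumed) and 80% power. The second rate is 0.45 × 0.65 = 0.2925, and the mean rate is 0.37125. The pooled-variance formula is

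n = [1.96 √(2 p̄(1−p̄)) + 0.8416 √(p₁(1−p₁) + p₂(1−p₂))]² / (p₁−p₂)²

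This gives 146.5, so 147 per arm, which agrees with the stated 150. (The rounded 30% gives 163 per arm; that is a separate matter.) The cohort size thus comes from the opioid-use outcome alone.

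**2. Number per arm for respiratory events.** These events are recorded in the recovery room, before post-discharge loss to follow-up. The relevant number is therefore nearer the roughly 187 randomized per arm (375 / 2) than the 150 evaluable at 30 days. Figures for 150 are shown for comparison.

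**3. Power to detect a doubling.** The documents give no event rates, so these are assumed. With d = p₂ − p₁,

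power = Φ[(d − 1.96 √(2p̄(1−p̄)/n)) / √((p₁(1−p₁) + p₂(1−p₂))/n)]

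For 5% to 10% and n = 187, this is Φ[(0.05 − 1.96 × 0.02724) / 0.02712] = Φ(−0.125) = 45%.

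| Assumed rates | n = 187 | n = 150 | Fisher exact, n = 187 |
|---|---|---|---|
| 2% to 4% | 20% | 17% | 12% |
| 5% to 10% | 45% | 38% | 38% |
| 10% to 20% | 78% | 68% | not computed |
| 15% to 30% | 94% | 88% | not computed |

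**4. What zero events would show.** The exact two-sided 95% upper bound is 1 − 0.025^(1/n): 2.0% for n = 187 and 2.4% for n = 150.

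**5. What an interval could show.** With equal true rates p in both arms and n = 187, the half-width of the 95% interval for the risk difference is 1.96 √(2p(1−p)/187). The smallest limit that the upper bound would fall below with 80% probability is (1.96 + 0.8416) √(2p(1−p)/187).

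| Assumed common rate | Half-width (points) | Smallest limit met with 80% probability (points) |
|---|---|---|
| 2% | 2.8 | 4.1 |
| 5% | 4.4 | 6.3 |
| 10% | 6.1 | 8.7 |

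These describe what one cohort can deliver. They are not proposals for what counts as similar.

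**The case against.** Several points on the other side are sound.

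- **Exploratory status.** These outcomes are exploratory, and such outcomes do not normally need a margin or a power statement. That stands, and no sample-size change is asked for. It also means that they should not carry a conclusion of similarity or established safety.
- **Expected decrease.** Section 2.3 also expects side effects to fall, and a difference test addresses that. True, but it leaves the similarity alternative without a test.
- **Logistic models.** A reader of the Synopsis alone might infer that chi-squared or Fisher tests are the only analysis. Section 2.8 adds adjusted logistic models, which yield an effect estimate and normally an interval. The plan does not commit to reporting that interval or say how it would bear on similarity.
- **No stated decision rule.** A reader might infer that a p-value above 0.05 will be taken as proof of similarity. No section says so. Section 2.2 shows that reading of earlier data, but it is background and not an analysis rule for this trial.
- **Section 3.0 explains the age limits.** A reader might infer a formal safety objective. The sentence only places possible later studies after safety is established here. It presupposes that outcome and does not make it an endpoint.
- **Low power is not certain.** A reader might infer that respiratory events are rare and that a doubling would probably be missed. The documents give no rate, and the four event types in section 2.6.7 are broader than naloxone use. At 10% to 20% a doubling would more probably be detected than missed.

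**Conclusion.** The concern holds. Section 2.3 includes similarity in the hypothesis and section 3.0 presupposes established safety, yet the planned comparisons test for differences in exploratory outcomes, cohort by cohort, without an interval criterion. As written, the plan cannot support the similarity half of the hypothesis. This conclusion does not depend on any event rate.

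How uninformative a non-significant result would be does depend on the rate, which has to be assumed. With about 187 per arm, a doubling would more probably be missed than found at control rates of 2% or 5% (power about 20% and 45%), and more probably found than missed at 10% (about 78%). These figures assume two-sided 0.05 and a normal approximation; Fisher's test gives less at the two lower rates (12% and 38%).

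The documents do not support the stronger claim that the plan itself would convert a non-significant result into a finding of safety or a warrant for studies in older patients. The primary and secondary outcomes, the sample size and the conduct of the trial are unaffected.

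**What to change.** 1. **Aim 3, section 2.8.** For each of the four respiratory-specific events, and for any of them, report the methadone-minus-control risk difference with a 95% confidence interval in each cohort.
2. **Use of the word similar.** Allow it only if the upper confidence limit lies below a difference that the investigators specify and justify before unblinding. If none is specified, or the limit is not met, report the result as descriptive.
3. **Optional cohort-stratified estimate.** Label it supplementary, because the cohorts are analyzed separately and receive different methadone regimens. With about 375 per arm across both cohorts, and assuming the same rates in each, power for 5% to 10% would be about 74%, against 45% in one cohort.
4. **Section 3.0.** Say that the trial will provide an estimate and an upper bound for respiratory events, in place of saying that it establishes safety.

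The cost is analysis-plan wording and one table, with no extra patients or assessments. The investigators must also agree a difference in advance if they wish to claim similarity. The drawback is a more modest safety conclusion.
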